At least 15% of people are clinically obese at the time of MS diagnosis.¹ Obesity is also a risk factor for the conversion of radiologically isolated syndrome (RIS) (early MS) to first attack and negatively influences MS functional outcomes and disability.²⁻⁴ Ocrelizumab is increasingly the disease modifying treatment of choice for people with MS in the USA and globally. Many Ocrelizumab-treated patients are starting to administer (with or without physicians' guidance) the glucagon-like peptide-1 (GLP-1) agonists⁵, such as semaglutides, for diabetes, weight loss, and an increasing number of FDA-approved and experimental indications. Many other patients with MS would like to start this drug class to induce weight loss. Others may be influenced by early phase data that suggest the GLP-1 medication class is neuroprotective, reduces cardiovascular disease risk, and/or allows weight maintenance to return to regular aerobic physical activity.⁶⁻⁸

Study Significance and Motivation

Although there is growing interest in understanding how metabolic interventions may intersect with immunotherapies in MS nearly no data exist on the co-treatment of people with MS with Ocrelizumab and a GLP-1 agonist (e.g. Wegovy). In 2023-24, we performed a small, retrospective study of ~50 people with MS and their weight loss and tolerability of GLP-1 agonists in Boston, many of whom were treated with Ocrelizumab (Udawatta et al. *Neurology Sci.* 2024 doi: 10.1007/s10072-024-07701-7).⁹ Others have followed with observational data on GLP-1 in cohort studies or have work in progress.^{10,11}

However, the sample sizes in existing published work are so far too small to conclude the outcomes of MS patients treated specifically with Ocrelizumab. Also, patient-based assessments and reports were lacking as early work has been largely retrospective and spanning the time when the GLP-1 agonists were only approved for MS patients with comorbid diabetes mellitus.

RESEARCH DESIGN AND METHODS:

Study Aims

In this prospective study, there are two main aims:

- (1) To implement patient-reported outcome measures (PROMs) in **60** people with MS already treated with both Ocrelizumab and a GLP-1 agonist to assess progression and ambulation, while recording drug tolerability and potential adverse events, weight loss, disease-based outcomes focused on progression, and MS-focused quality of life; and

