Participants will be enrolled for an estimated 72 weeks: Measurements will be requested every four weeks (i.e. q28 days) on a specifically designed survey instrument for MS participants. Participants will be asked to report medication dosing, adherence to medicine, tolerability, weight, height, and exercise activities. Self-reported scales will be administered to the participants as well (measuring disability, fatigue, mood, and quality of life).

Participants must be currently on Ocrelizumab (last dose within the past <6 months) and currently taking a GLP-1 medication.

Participants will be contacted and interviewed via Zoom every 6 months to ensure study procedures are going as planned, verify data reported on medication and MS disease history, and ensure study procedures are operating smoothly. Participants who do not complete the surveys within 7 days of the scheduled timing will be contacted by a study coordinator by phone up to 3 times. Participants will also be asked to report any medication changes, dose changes, or discontinuations if they occur at any point between study visits.

Participants will be enrolled until a total of 40 individual participants are reached. Study procedures for each group are listed in Tables 1 and 2. All scheduled events will be part of the study and not part of routine clinical care.

Table 1: Measurements of MS Participants in Aim 1 (Cohort): Frequency and Scale

Measure	Frequency of Reporting	Scale
Weight	Monthly	kg or lbs
Height	Baseline	cm or inches
Waist, Hip, Limb Circumferences	Monthly	cm or inches
Ambulation score	Monthly	Kurtzke Scale
Disability Score	Monthly	PDSS
Step Count	Monthly	Average daily number on phone or step counter if available
Fatigue	Monthly	Fatigue Severity Scale
Mood	Monthly	Beck Depression Inventory
Quality of Life	q3 months	MS-QOL-54 survey
Intolerabilities	Monthly	Self-reported, qualitative, categorized – gastrointestinal, injection site, infections, etc.
Adherence	Monthly	Number of doses taken/ Total Prescribed doses of GLP-1
Axonal degeneration	Baseline and end of study (if possible)	Neurofilament light chain (serum)
New attacks or lesions	Ad hoc	Reported event if occurs

Table 2: Measurements of MS Participants in Aim 2 (Single-Arm Open-Label Trial)

	Screening	Baseline	Week 24	Week 48	Week 72	Unscheduled Visit (e.g. Relapse, Early Withdrawal)
Clinical & MS Relapse History	X	X	X	X	X	X

Medication Review	X	X	X	X	X	X
Physical Examination	X		X	X	X	X

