Waist, Hip, Limb Circumferences		X	X	X	X	X
Skin Fold Thickness		X	X	X	X	X
Neurological Examination	X	X	X	X	X	X
EDSS & Ambulation Score		X	X	X	X	X
Vital Signs (ht, wt, BMI, blood pressure, heart rate, respiratory rate)	X	X	X	X	X	X
PDDS		X	X	X	X	X
PROMS		X	X	X	X	X
QOL54-MS		X	X	X	X	X
Medication Adherence Questionnaire (GLP-1-focused)		X	X	X	X	X
25-foot timed walk test		X	X	X	X	X
Food Frequency Questionnaire		X	X	X	X	X
Physical Activity Questionnaire		X	X	X	X	X
9-Hole Peg Test		X	X	X	X	X
SDMT+PASAT		X	X	X	X	X
Blood Draw: CBC/differential +Chemistry	X					X
NFL-2, plasma		X	X	X	X	X
GFAP, blood		X	X	X	X	X
Vitamin D		X				X
Beta-HCG (urine) (invoiceable)	(X)	(X)	(X)	(X)	(X)	(X)
MRI Brain, 1.5T (not billed to study)	X	X			X	X

Allocation and Blinding

All participants will be treated with the two drugs of interest: Ocrelizumab and the GLP-1 agonist. The participants will be blinded to the study outcome of interest, i.e. progression or PIRA. The investigators will not be blinded to the study outcome. The participants will not have access to their prior PDDS scores on file, earlier in the study. The EDSS raters will not have access to the prior EDSS scores on file, earlier in the study. The statisticians will not be blinded to the study outcome.

Criteria for Study Drug Discontinuation in a Single Participant

Reasons for GLP-1 agonist drug discontinuation will be at the discretion of the treating prescriber include: (1) laboratory test abnormalities (e.g. transaminitis) whether related to the drugs or not; (2) intercurrent illness; (3) severe intolerance to the GLP-1 agonist; (4) lack of access to the GLP-1 drug within an affordable range; (5) patient preference; (6) achieved weight target earlier than anticipated; or (7) any other reason as determined by the prescribing physician or study principal investigator.

Criteria for Study Withdrawal of a Participant

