Participants who discontinue GLP-1 agonist drugs for any reason, including tolerability, cost, desired weight loss outcome, etc., will continue to be observed until the end of the study period. It is possible that participants will have periods of discontinuation and then resume GLP-1 agonist treatment. The participant will be observed until (a) week 72 visit (i.e. end of study period), (b) participant withdrawal with no consent to continue monitoring, or (c) investigator-decided withdrawal of a participant from the study (e.g. severe medical illness preventing study completion, departure far from study site, etc.).

Participant Compensation for Involvement in Research Procedures

Aim 1: Each participant will receive 75 USD every 3 months with a total of up to **600 USD**.

Aim 2: Each participant will receive 150 USD at baseline and 100 USD every subsequent visit occasions and then 150 USD at the final study visit with a total of up to **500 USD**.

Participants will have the option to receive cash or a gift card. Participants who receive cash will need to provide their social security number for the reporting of taxable income to the Internal Revenue Service, according to applicable laws.

There is no anticipated drug development or future product anticipated in this study. A study participant will not have any right to compensation or ownership interest related to such development.

RISKS AND BENEFITS:

Risks to Participants

Participants in this study may have side effects of the medications under investigation including both Ocrelizumab and the GLP-1 medication, although these will be given in the context of clinical care for U.S. Food and Drug Administration (FDA)-approved indications. In particular, the GLP-1 class of medications is known to cause gastrointestinal symptoms, including nausea, vomiting, early satiety, and abdominal discomfort. These are considered reversible, common (approximately 1/3 of all people treated with a GLP-1 medication), and expected. These risks are often mild to moderate and in some cases may lead to early discontinuation of the medication if poorly tolerated. Participants may experience injection-site reactions which could be bothersome.

An additional risk is that participants will be psychologically burdened by repeated testing and surveying throughout the study; however, no clinical harm is anticipated from surveys or the clinical assessments done during the study procedures.

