Variables of interest will be reported using descriptive frequency-based statistics (e.g. mean, median, range). Subgroups of interest (e.g. by gender, disability level below or above the median, etc.) will be compared using t-tests and tests of two proportions as appropriate. Repeated measures (e.g. weight) will be graphed and displayed. Change in values will be reported (final minus starting weight). If needed to report an outcome, repeated measures analyses, will be made using generalized linear models. Incidence of tolerability issues will be reported as the number of events per number of person-months of observation available.

Aim 2:

This will be an intention to treat analysis. All participants who enroll in the single-arm study will be analyzed to the end of their study participation, either the end of the planned study period or time of withdrawal. Data will be analyzed in aggregate with descriptive subgroup analyses performed with the following variables and subgroupings of interest: (1) sex at birth, (2) age at enrollment below or above the median age, (3) duration of GLP-1 (72 weeks versus early discontinuation), (4) BMI group (<30.0 kg/m², 30-39.9 kg/m², >40.0 kg/m², and (5) EDSS score at enrollment above or below the median.

The primary outcome measure is PIRA, dichotomized as present or not, as measured by the rater-determined composite functional outcomes score. This includes the EDSS score with contributions by the 9-hole peg test, SDMT, and 25-foot walking test, and will be constructed as presented in the ORATORIO trial for Ocrelizumab in primary progressive MS vs. placebo.

EDSS will be measured pre-GLP-1 (enrollment) and at the participant's end of study (i.e. one of (a) the end of planned study enrollment period, (b) administrative withdrawal, or (c) participant withdrawal). A positive change in EDSS score of 1.0 points with a baseline EDSS of <5.0 or a positive change in EDSS score of 0.5 points or more with a baseline EDSS score of 5.0 or higher will be considered PIRA. EDSS will be captured at each study visit but the first and last EDSS scores will contribute to the assessment of PIRA for the primary study outcome's hypothesis testing. The use of the EDSS scores at each q24week study visit will also be used in a generalized linear model to determine disability level worsening at any timepoint.

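### Aim 1 tolerability rate is set per person-month of all observation, so for events rarer off GLP-1 it sits below the on-drug rate by an unknown amount

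*Protocol*

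**What the plan says.** Study Aims describes Aim 1 as administering patient-reported measures "while recording drug tolerability and potential adverse events, weight loss, disease-based outcomes focused on progression". The Aim 1 analysis text, under Data Management and Confidentiality, then gives one tolerability measure: "Incidence of tolerability issues will be reported as the number of events per number of person-months of observation available". The protocol states no rate restricted to time on GLP-1.

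Four other places bear on that denominator.

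- **Criteria for Study Withdrawal of a Participant.** People who stop GLP-1 for any reason, tolerability among them, "will continue to be observed until the end of the study period". The same section adds: "It is possible that participants will have periods of discontinuation and then resume GLP-1 agonist treatment". It is not limited to one aim.
- **Criteria for Study Drug Discontinuation in a Single Participant.** The listed reasons include "severe intolerance to the GLP-1 agonist", alongside cost or access, preference and reaching the weight target.
- **Risks to Participants.** Gastrointestinal symptoms are attributed to the GLP-1 class and called reversible. The side effects are described as often mild to moderate and in some cases "may lead to early discontinuation of the medication if poorly tolerated".
- **Study Procedures, Aim 1.** "Participants will be asked to report medication dosing, adherence to medicine, tolerability, weight, height, and exercise activities". Discontinuations between contacts are also to be reported, and Table 1 records intolerabilities by category and GLP-1 adherence every month.

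The Aim 2 analysis text names a subgroup by "duration of GLP-1 (72 weeks versus early discontinuation"). The Aim 1 text names no such split.

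**The concern.** A reader will take an Aim 1 tolerability rate as the rate of events while using GLP-1 with ocrelizumab. The denominator also counts months in which the participant was not taking GLP-1. One route into those months is the very kind of event being counted, because intolerance is a listed reason to stop.

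For event types that subside once the drug is stopped, the off-drug months add person-time but few events, and the reported figure falls below the on-drug rate. The figure could then be quoted as on-drug tolerability, or set beside on-treatment rates from elsewhere, and read too low.

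A smaller labelling matter sits in the same paragraph. Weight change is defined as the last value minus the first. In people already on GLP-1 at entry, this most naturally means change since enrolment, not change since starting the drug.

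**Working it through.** The protocol states no tolerability rate, discontinuation rate or precision target, so there is no figure of its own to reproduce. The check is an identity plus illustrations.

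**Inputs from the protocol.** Aim 1 follow-up is 72 weeks with surveys every four weeks, so 72/4 = 18 intervals per person. Aim 1 size is 60 in Study Aims and Participant Population(s), giving at most 60 × 18 = 1,080 four-week person-months. The Aim 1 procedures also give an enrolment total of 40, which would make it 40 × 18 = 720. The ratios below do not depend on which holds.

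**Assumed inputs.** The on-drug rate L, the off-drug rate rL, and the off-drug share of person-time f.

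**Identity.** All-observation rate = (1 − f)L + f·rL = L[1 − f(1 − r)]. The relative understatement of the on-drug rate is therefore f(1 − r). It is positive when r < 1, zero when r = 1, and negative (an overstatement) when r > 1.

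| f | r = 0 | r = 0.5 | r = 1 |
|---|---|---|---|
| 5% | 5% | 2.5% | 0% |
| 10% | 10% | 5% | 0% |
| 20% | 20% | 10% | 0% |
| 30% | 30% | 15% | 0% |

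**What these values of f require.** If a share d stops for good at mid-follow-up, f = d/2. So f = 5%, 10%, 20% and 30% need 10%, 20%, 40% and 60% of participants to stop. If they stop at week 24 instead, f = d × 48/72, so d = 10%, 20% and 30% give f = 6.7%, 13.3% and 20%.

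**Worked example (assumed values).** Take 60 people, with 30% (18 people) stopping for good at week 24. Off-drug time is 18 × 12 = 216 intervals and on-drug time is 1,080 − 216 = 864, so f = 0.20. With L = 0.10 per person-month there are 86.4 on-drug events.

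- r = 0: planned rate 86.4/1,080 = 0.080; on-drug rate 86.4/864 = 0.100. The planned rate is 20% lower.
- r = 0.5: 10.8 further events off drug; planned rate 97.2/1,080 = 0.090, or 10% lower.
- r = 1: 21.6 further events; planned rate 108/1,080 = 0.100, no difference.

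**Does more stopping lower the reported figure?** With L held fixed and r < 1, yes. If tolerability worsens, L is likely to rise together with f. At r = 0, moving from f = 5% to f = 20% leaves the reported rate unchanged when L rises by a factor 0.95/0.80 = 1.19. A larger rise in L raises the reported rate and a smaller one lowers it.

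**Precision of an on-drug rate.** Under Poisson counts, its relative standard error divided by that of the planned rate is √[(1 − f + fr)/(1 − f)]. At r = 0 this is 1.00. At r = 0.5 it is 1.03 for f = 10% and 1.10 for f = 30%. At r = 1 it is 1.05 and 1.20.

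**The case against.** The strongest reply is that nothing is misstated. A rate per observed month is legitimate, the protocol never calls it an on-drug rate, and Table 1's intolerabilities include infections, which need not depend on GLP-1. A separate analysis plan, not shown here, could add an exposure-based rate, and the Aim 1 subgroup list is open-ended. This stands in part: the planned rate is valid and worth keeping. It does not dispose of the point, because the protocol does fix a denominator for something it calls drug tolerability, and that denominator mixes on-drug and off-drug time.

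The size is also fairly disputed. Participants in a cohort described as already treated may have passed the period in which early stoppers leave, so f could be 5% or less. In the worked example, 86.4 events carry a Poisson relative standard error of about 1/√86.4 = 11%, larger than a 5% shortfall. This stands.

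Three stronger readings are tempting, and the protocol does not support them.

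- **A reader might infer that worse tolerability will show up as a lower rate.** That follows only for a given on-drug rate. The net direction when tolerability worsens is not established.
- **A reader might infer that Aim 1 will certainly include people off GLP-1 from entry.** Additional inclusion criterion 8 would admit recent past users and people about to start, but the Aim 1 procedures require current use. This is an unresolved conflict, not established off-drug time.
- **A reader might infer that the weight measure is wrong.** Change since enrolment is a sound measure; it only needs that label.

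**Conclusion.** The point holds in a limited form. The planned Aim 1 rate describes all observed time, and for event types rarer off drug it understates the on-drug rate by f(1 − r). The protocol's description of gastrointestinal symptoms as class-caused and reversible supports r < 1 for that category. For infections r may be close to 1, and then nothing is lost.

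The direction for drug-dependent events follows from the algebra. The size is unknown, because the protocol supplies neither f nor r; illustrative values run from nil at r = 1, through 5% at f = 5% and r = 0, to 20% at f = 20% and r = 0. The conclusion rests on reading the continued-observation rule as applying to Aim 1. Nothing exempts Aim 1, which also runs 72 weeks and asks participants to report discontinuations.

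Only a descriptive output is affected. The primary endpoints are not. The change is worth making because it is cheap and the measure serves a stated purpose of Aim 1.

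**What to change.** In the Aim 1 analysis text:

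1. Report, by Table 1 category, events during on-drug time per on-drug person-month, using the dosing and discontinuation reports already collected.
2. Prespecify how an interval containing a stop or restart is divided or classified, and a window after the last dose within which events and time still count as on drug.
3. Keep the all-observation rate alongside, and report how many participants stop GLP-1 and why.
4. State that events and stops before enrolment are not captured, so an on-drug rate does not remove the selection of people who tolerate the drug.
5. Label weight change as change since enrolment (minor).

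Separately from the denominator, two conflicts must be reconciled: additional inclusion criterion 8 for Aim 1 against the current-use requirement in the Aim 1 procedures, and the Aim 1 size of 60 against the 40 in those procedures.

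The cost is wording, a little more analysis work and a slightly less precise rate. For f between 10% and 30% the relative standard error is unchanged at r = 0, 3–10% larger at r = 0.5 and 5–20% larger at r = 1. No new assessments are needed.

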- (2) Enroll a single-arm, open-label trial of **40** Ocrelizumab-treated MS patients who are soon starting GLP-1 agonists, monitored prospectively for 2 years to measure MS **progression** (clinical disability worsening, stability or improvement) every 3 months, including (a) clinical assessments (e.g. EDSS, 25-foot timed walk, SDMT) as used in the ORATORIO trial of Ocrelizumab, (b) PROMs on progression in MS including fatigue, ambulation distance, mood; and (3) simple objective biomarkers of disease (e.g. plasma neurofilament light chain, glial fibrillary acidic protein).

Overview: Aims 1 and 2 will recruit participants simultaneously but draw upon MS participants at different points in their GLP-1 agonist treatment. Participants can enroll in either the cohort of Aim 1 (in-person or remote) or the open label trial of Aim 2 (in-person only), not both aims. All participants will be Ocrelizumab-treated for MS upon study enrollment.

Study Endpoints

The primary outcome measure is **PIRA** (progression independent of relapse activity), based primarily on clinical assessment, dichotomized as present or not.¹²

For Aim 1, the cohort, patient-derived disability status (PDDS) score, and ambulation score (self-reported) will be the primary endpoints of interest.

For Aim 2, the clinical trial, PIRA will be measured pre-GLP-1 start and at study end (week 72). A composite score of disability, similar to the ORATORIO¹³ trial will be constructed including EDSS score, 25-foot timed walk, 9-hole peg test, and SDMT score.

Study Interventions/ Investigational Agent

Glucagon-like peptide-1 agonist agent is the study agent of interest. This study will not supply the GLP-1 drug but depend on the patient's clinical prescription of this drug. Similarly, all participants will be treated with Ocrelizumab for the indication of MS; however, the study will not provide Ocrelizumab as it will be part of the participant's routine clinical care.

Study Procedures

Inclusion Criteria, Aims 1 and 2:

- 1) Diagnosis of MS (2019 revised McDonald criteria) of any type (PPMS, RRMS, SPMS) by a neurologist,
- 2) Adult age 18-70 years,
- 3) BMI $\geq 24.0 \text{ kg/m}^2$,
- 4) Taken at least one dose of Ocrelizumab prior to study entry,
- 5) EDSS < 7.0 ,
- 6) Able to provide individual informed consent,
- 7) MRI available to confirm the diagnosis of MS.

Exclusion Criteria, Aims 1 and 2:

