***Additional Inclusion Criteria Aim 2:**

- 8) Able to present for baseline and follow up in person,
- 9) Unexposed to a GLP-1 agonist in the past year,
- 10) Starting on a GLP-1 agonist in the next <6 months,
- 11) Plan to be exposed to GLP-1 agonist for a minimum of 72 weeks following enrollment.

Participant Population(s)

Accrual Number:	Category/Group:	Consented/Enrolled:
Local	Individuals with MS already treated with Ocrelizumab and GLP-1 agonist	60
	Ocrelizumab-treated MS patients initiating GLP-1 agonist	40
Study-wide		
Total:		100

RECRUITMENT METHODS:

Potential participants will be identified through online research advertising webpages (e.g., ClinicalTrials.gov, Northwestern's clinical trials website), the investigator's connections with MS neurologists in the practice and surrounding practices, advertisements in MS clinics, the National MS Society local chapter's and national websites, MS physician networks, social media directly to patients, flyers in the medical infusion center, weight loss and nutrition clinics in the region, and through clinic newsletters and the word of mouth.

Interested patients will be screened through an online RedCap™ form for the study's eligibility criteria. Medical records review will occur by the investigators to ensure the criteria are met. Participants will then be called by telephone or met in person to describe the study procedures in detail.

CONSENT PROCEDURES:

Consent will be taken by a trained study team research coordinator or physician. All consent will be written on a standardized consent form, in English. Consent may be performed electronically using REDCap e-sign with an institutionally approved account. Participants will be given >24 hours to review the consent form and provide consent. Given the complexity of the study tasks including multiple self-reported variables, only participants who are able to provide their own consent will be enrolled.

Vulnerable Populations

Vulnerable populations will not be enrolled. Participants who lack capacity to voluntarily consent (e.g. institutionalized, dementia) are excluded as per the criteria listed above.

STUDY PROCEDURES:

Aim 1 will allow fully remote participation, drawing from geographically diverse settings throughout the USA. Participants in Aim 1 do not need to visit the study site in person or be

independently mobile but must be continuously available during the study timeframe remotely for PROMs and study surveys and calls.

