Variables that will be collected or measured, as potentially related to the endpoints of interest, include: subtype of MS (relapsing remitting, primary progressive, secondary progressive), prior DMT use (number of prior DMTs, names), history of relapse of MS in the prior 1 year, highest body weight in the prior year, average body weight in the preceding year, comorbid diagnoses (diabetes mellitus, cardiovascular diagnoses, psychiatric (present/absent, duration)), concomitant medications (particularly those that may affect body weight), smoking status (cigarette), alcohol intake (amount), etc.

Regression variables of interest for the outcome of PIRA will be assessed using exploratory univariate regressions of individual variables of interest. These variables will be determined *a priori* and include sex assigned at birth, age at baseline, BMI at baseline, EDSS at baseline, duration of MS disease (from diagnosis), duration of Ocrelizumab (Ocrevus) treatment.

Secondary endpoints will include (1) a change in 25-foot timed walk, (2) MS-QOL-54 scores, and (3) neurofilament light chain levels.

Sample size justification: The proportion of people with PIRA on GLP-1 agonist drugs and Ocrelizumab is unknown. The proportion of patients with PIRA in relapsing MS ranges up to 24% in published reports.¹⁴ In this study, the detectable difference between a known proportion of patients with PIRA and our study group is $\geq 10\%$, with alpha=0.05 and power=0.8. Since participants will not be randomized to no treatment or intentionally discontinued on GLP-1 agonist treatment during the study, there is no comparison group.

All approved data storage platforms, back-up and recovery procedures, and data access controls will be performed in accordance with the data storage policy at Feinberg School of Medicine: <https://www.feinberg.northwestern.edu/it/policies/file-storage.html>

Provisions to protect the privacy interests of participants:

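### The Aim 2 primary set is everyone who enrols, so any participant who never starts the GLP-1 agonist would count in a proportion meant to describe co-treatment

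*Protocol*

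**What the plan says.** The Aim 2 paragraphs under Data Management and Confidentiality fix the analysis set: "This will be an intention to treat analysis", and "All participants who enroll in the single-arm study will be analyzed to the end of their study participation". Membership depends on enrolment alone. EDSS change for PIRA also runs from enrolment.

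The Additional Inclusion Criteria for Aim 2 put enrolment before exposure. Entrants must be "Unexposed to a GLP-1 agonist in the past year" and "Starting on a GLP-1 agonist in the next <6 months", with the further condition "Plan to be exposed to GLP-1 agonist for a minimum of 72 weeks following enrollment". The last two are plans at entry, not conditions for being analysed.

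Under Study Interventions/Investigational Agent, "This study will not supply the GLP-1 drug"; the section on Economic Burden to Participants adds that the study does not pay for it either.

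Two other places treat exposure as certain. Allocation and Blinding says "All participants will be treated with the two drugs of interest: Ocrelizumab and the GLP-1 agonist". The sample size justification gives as the unknown quantity: "The proportion of people with PIRA on GLP-1 agonist drugs and Ocrelizumab is unknown".

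**The concern.** The question is about people taking both drugs, but the set does not require that the second drug is ever taken. Enrolment rests on an intention to start, and the start depends on a prescription obtained and paid for outside the study. A participant could therefore complete 72 weeks without a dose and still be counted.

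Keeping untreated people normally protects a randomised comparison. Here there is one arm, and the sample size justification itself says there is no comparison group, so that reason does not apply. What remains is possible dilution: never-starters would pull the estimate toward background risk. That could hide a benefit. It could equally hide harm, which matters because the section on potential benefits expects the study to establish the safety of the combination.

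**Working it through.** **1. Is a never-starter handled anywhere?**

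- Criteria for Study Withdrawal keeps under observation those who discontinue the GLP-1 agonist. It is silent on those who never begin.
- The only exposure subgroup in the Aim 2 analysis contrasts 72 weeks of GLP-1 with early discontinuation. A never-starter has no level, and a late starter fits neither level well.
- Withdrawal by the investigator does not remove a never-starter, because withdrawn participants are analysed up to withdrawal.
- The Study Procedures sentence requiring current GLP-1 use belongs to the Aim 1 description. It cannot apply to Aim 2, whose entrants must be unexposed in the past year.

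No section requires a first dose for inclusion in the analysis.

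**2. Inputs**

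- N = 40 (Aim 2), alpha 0.05, power 0.80 and a difference of at least 10 points, all from the protocol. Direction and sidedness are not stated.
- Reference PIRA proportion p0 = 24%, given as the upper end of published reports in relapsing MS.
- On-drug proportion p1 = 14% or 34%, which is 24% minus or plus the protocol's 10 points.
- Share of enrolled people who never start, f: not in the protocol. Assumed 5% to 30%.

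**3. The protocol's own figure**

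One-sample test against a fixed p0, normal approximation:

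n = [(z_α·√(p0(1−p0)) + z_β·√(p1(1−p1))) / |p1−p0|]²

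For 24% against 14%, two-sided: [(1.960 × 0.427 + 0.842 × 0.347) / 0.10]², which gives 128. For 24% against 34% it gives 153. At N = 40 the two-sided power is 27.8% and 33.3% respectively. The stated 10-point detectable difference is therefore not reproduced at N = 40 with p0 = 24%. That is a separate matter and is no evidence for this point; the 24% and 10 points serve below only as a scale.

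**4. Dilution**

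If never-starters progress at p0:

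p(all enrolled) = (1−f)·p1 + f·p0, so the difference from p0 is (1−f)·(p1−p0).

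Example, f = 10%: 0.90 × 14% + 0.10 × 24% = 15.0%, a difference of 9 points.

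| f | Never-starters of 40 | All enrolled, p1 = 14% | Difference left (points) | All enrolled, p1 = 34% | Power, all enrolled (p1 = 14%) | Power, starters only (p1 = 14%) |
|---|---|---|---|---|---|---|
| 0% | 0 | 14.0% | 10.0 | 34.0% | 27.8% | 27.8% |
| 5% | 2 | 14.5% | 9.5 | 33.5% | 25.1% | 26.2% |
| 10% | 4 | 15.0% | 9.0 | 33.0% | 22.7% | 24.7% |
| 20% | 8 | 16.0% | 8.0 | 32.0% | 18.3% | 21.7% |
| 30% | 12 | 17.0% | 7.0 | 31.0% | 14.7% | 18.7% |

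Power is two-sided. Starters-only power uses n = 38, 36, 32 and 28.

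**5. Scale against sampling error**

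The standard error of 14% at n = 40 is √(0.14 × 0.86 / 40) = 5.5 points. The shifts of 0.5 to 3 points are all smaller than that.

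**6. Late starters**

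Taking 6 months as about 26 weeks, a start at the limit leaves 72 − 26 = 46 weeks on drug, or 46/72 = 64% of follow-up. A first-dose rule does not remove this unexposed time.

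**The case against.** A reader might infer that the primary set will contain never-starters, and hence that the Aim 2 proportion fails to describe co-treatment. The protocol does not support that. It nowhere says that never-starters will occur. Entrants must expect to start and must plan 72 weeks of exposure, and the investigator may exclude anyone thought unable to complete study activities. Lack of affordable access is listed as a reason for stopping the drug, so it is only indirect evidence about never starting. If everyone starts, the all-enrolled set and the treated set are the same people.

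The size is also soft. The never-start share is assumed. The 24% is an upper figure for relapsing MS, while Aim 2 also admits progressive disease. The shifts lie within one standard error, and restricting to starters recovers little power.

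Analysing everyone enrolled can be defended as describing what happens to people who plan co-treatment under usual care, and it fits the policy of observing discontinuers to week 72. That policy is deliberate and is not at fault here. But it covers people who have begun treatment, and the sample size section asks about people on both drugs, not people planning to be.

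Finally, a set defined by first dose is selected on an event after enrolment: people who withdraw, fall ill or worsen before starting drop out. This stands, and is why the all-enrolled result should be kept as a sensitivity analysis. Set definitions are often left to an analysis plan, but here the protocol fixes the set itself, so the rule can be judged as written.

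**Conclusion.** The point holds in conditional form. The stated set admits never-starters, nothing handles them, and the sections on inclusion, analysis, allocation and sample size do not agree on whether everyone analysed is exposed. With no randomised comparison to preserve, counting unexposed people does not serve the stated question.

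The size is unknown. Each 10% of never-starters removes about 1 point of a 10-point on-drug difference in either direction. This assumes that never-starters progress at 24% and that on-drug PIRA is 14% or 34%. With none, there is no effect. The case for the change rests on a clear target and a very low cost, not on a large expected bias. The rule should be set before data accrue, because investigators and statisticians are not blinded to outcome and interim analyses run every 6 months.

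**What to change.** In the Aim 2 analysis text:

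- Define the primary set as enrolled participants with at least one GLP-1 agonist dose, kept regardless of later discontinuation.
- Report never-starters separately, with number and outcome.
- Keep the all-enrolled result as a sensitivity analysis.
- Drop the intention-to-treat label.
- Record the first-dose date at the medication review already scheduled in Table 2, and report time from enrolment to first dose.
- Reconcile the statement under Allocation and Blinding that all are treated with the Aim 2 inclusion criteria and the analysis set.

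The cost is wording and one data field. The downsides should be stated in the protocol: the set may be slightly smaller, it is selected on a post-enrolment event, and late starters still contribute unexposed time because PIRA is measured from enrolment.

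Replacing never-starters should not be required. At a 30% share, 40 starters would need about 40/0.70 = 57 consents. The 17 extra would take roughly 4 to 6 months at the planned 3 to 4 per month, before counting the wait to establish that someone has not started.
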